## **2.2 Rationale for Primary Objective and Study Design**

The long-term safety profile of pridopidine is not known. For patients previously having taken part in a clinical study, an open-label observational study is the most appropriate study design.

### 2.3 Rationale for Dosage Used

Patients entering this study were treated with either 0 (placebo), 10, 22.5 or 45 mg pridopidine bid in the HART study, or 0 (placebo), 45, 67.5, 90, or 112.5 mg pridopidine bid in the PRIDE-HD study.

The proposed dose selected for this study is pridopidine 45 mg bid. The proposed dose has been evaluated in 3 large HD clinical studies (HART, MermaiHD, and PRIDE-HD) as well as 2 open-label extension studies (Open-HART and Open-PRIDE-HD) and has been generally well tolerated. In PRIDE-HD, 45 mg bid was the lowest of 4 doses evaluated. [REDACTED]

[REDACTED] Thus, from a benefit-risk perspective, the Sponsor sees no benefit in continuing to explore doses higher than 45 mg bid. [REDACTED]

[REDACTED] Thus, the Sponsor sees no therapeutic benefit at exploring doses lower than 45 mg bid.

Both pharmacokinetic data and clear dose-dependent and exposure-dependent QTc findings in PRIDE-HD rule out systematic dosing errors. While the HART and MermaiHD studies had explored the clinical profile of doses up to 45 mg bid, PRIDE-HD was designed to test the high end of exposure on potential clinical benefit (Food and Drug Administration [FDA] Type C meeting; 24 July 2013).

The integrated safety analysis and large safety database from the double-blind, placebo-controlled HART, MermaiHD, and PRIDE-HD studies indicated that the AE profile of pridopidine 45 mg bid is generally well tolerated and comparable with placebo. [REDACTED]

The integrated analysis of data from the double-blind, placebo-controlled HART, MermaiHD, and PRIDE-HD studies indicated the following:

- [REDACTED]
- [REDACTED]
- [REDACTED]
- [REDACTED]
- [REDACTED]
- [REDACTED]

### **3 OBJECTIVES**

The objective is to assess the long-term safety of pridopidine and to analyze treatment effects during long-term, open-label treatment.

#### **3.1 Primary Objectives**

The primary objectives are to assess the long-term safety of pridopidine treatment and to collect information on Unified Huntington's Disease Rating Scale (UHDRS) development during long-term, open-label treatment.

#### **3.2 Exploratory Objective**

The exploratory objective is to evaluate patient and site staff satisfaction with virtual study visits and remote assessments administered in adult patients with HD.

### **4 STUDY DESIGN**

This is a multi-center, open-label study of pridopidine 45 mg bid for patients who completed the HART or PRIDE-HD studies and who transitioned from the Open-HART pre-virtualization study period.

#### **4.1 Centers**

Multiple Huntington Study Group (HSG) sites will take part in the virtual aspect of this ongoing study in the US and Canada.

#### **4.2 Patient and Unique Identification Numbers**

Each patient is provided a patient identification number. These numbers are used in consecutive order by the site from the site-specific patient identification list provided to the site by the Clinical Trials Coordination Center (CTCC); this four-digit number will identify patients on all study documents and lab specimens. All PRIDE-HD patients have been provided with a new patient identification (ID) number. Patient ID numbers will be documented in the database for future reference. Each patient has a CTCC Unique ID Number that was issued during the HART (ACR16C009) or PRIDE-HD study (TV7820-CNS-20002). This number will enable the CTCC to track individual patients across multiple studies without storing any personally identifiable information.

#### **4.3 Recruitment**

This study is open to all patients who have successfully completed the HART (ACR16C009) or PRIDE-HD (TV7820-CNS-20002) studies and transitioned from the Open-HART pre-virtualization study period. No other patients will be recruited into the study.

#### **4.4 Inclusion Criteria**

- Patient is able to and has provided written Informed Consent prior to all study-related procedures.
- [Revision 1] Patient has completed the HART (ACR16C009) or the PRIDE-HD (TV7820-CNS-20002) studies and had remained on IMP during the full on-treatment part of the study (including de-escalated patients) or has transitioned from the Open-HART pre-virtualization study period.
- Patient is willing and able to take oral medication and able to comply with the study specific procedures.
- Patient is not participating in another clinical study of an investigational intervention.

- [New criterion] Patient has a wireless internet connection at home (and/or applicable locations) at the first remote visit.
- [New criterion] Patient has the ability to transition from in-person study visits to virtual study visits. The first remote visit (RV1) will take place within approximately 30 days after the last in-person visit.

#### 4.5 Exclusion Criteria

- [Revision 1] Ongoing treatment with tetrabenazine or deutetrabenazine, seizure threshold lowering medications, or certain antipsychotics and antidepressants (see Protocol Section 5.7 and current Operations Manual for list of disallowed medications).
- [Revision 2] Newly instigated or changed treatment with neuroleptics/anti-psychotics.
- [Revision 3] Use of tricyclic antidepressants or class I & III antiarrhythmics at any time during the study period.
- [Revision 4] Any clinically significant, abnormal laboratory result, including clinically significant hepatic or renal impairment, or any ongoing AE that, in the opinion of the investigator (or qualified designee), affects the patient's suitability for the study or puts the patient at risk if he/she continues in the study.
- [Revision 5] A prolonged QTc interval at the RV1 (defined as a QTcF interval of >450 ms for both males and females using Fredericia's formula) or other clinically significant heart conditions as judged by the investigator (or qualified designee).
- [Revision 6] Severe intercurrent illness that, in the opinion of the investigator (or qualified designee), may put the patient at risk when continuing participation in the study.
- [Revision 7] Alcohol and/or drug abuse as defined by the Diagnostic and Statistical Manual - Fourth Edition - Text Revision criteria for substance abuse – this includes the illicit use of cannabis.
- Patients with AEs of suicidal ideation or attempt at any time in the past or as measured by a suicide ideation score of  $\geq 3$  on the Columbia-Suicide Severity Rating Scale (C-SSRS) (who answer "Yes" to questions 3, 4, and 5 in the scale suicidal ideation section), or a score of  $\geq 3$  on the Problem Behaviors Assessment – Short Form (PBA-s), or patients who answer "Yes" on any of the 5 C-SSRS Suicidal Behavior Items (actual attempt, interrupted attempt, aborted attempt, preparatory acts, or behavior), if an attempt or acts were performed at any time in the past, or patients who, in the opinion of the investigator (or qualified designee), present a risk of suicide.
- Patients with a known history of epilepsy or a history of febrile seizure(s) or seizure(s) of unknown cause.
- Females who are pregnant or lactating.
- Females who are of child bearing potential and not taking adequate contraceptive precautions (either oral, barrier, or chemical contraceptives) are excluded from the study. Females of child-bearing potential taking acceptable contraceptive precautions can be included.
- Known allergy to any ingredients of the study medication (Please refer to the Investigator Brochure (IB) for a full ingredient list).
- [Revision 8] Creatinine clearance  $< 60$  mL/min at virtual transition visit (VTV), calculated using the Cockcroft-Gault equation:  $(140 - \text{age}) \times \text{mass (kg)} \times [0.85 \text{ if female}] / 72 \times \text{serum creatinine (mg/dL)}$ . It is allowed to repeat the test once, if clinically appropriate.

#### 4.6 Conduct of the Study

The ACR16C015 (Open-HART) open-label extension study began in 2011 and has been ongoing in the United States and Canada (see [Appendix 1](#)) to evaluate the long-term safety and tolerability of pridopidine administered at a dose of 45 mg bid in adult patients with HD

who completed the treatment period of the HART or PRIDE-HD studies. The primary reason for this amendment is to evaluate the feasibility of virtual study conduct and remote assessments administered in adult patients with HD receiving pridopidine 45 mg bid. All clinical sites will conduct study assessments remotely. The study will consist of a VTV, an open-label treatment period, and a follow-up period (30 days after end of treatment). The study will continue under the same study number; however, all patients will have to be re-consented regardless of their current study status. A CRO will provide oversight and many functions will be performed centrally. The study will include both remote visits and safety telephone contacts (TC). Remote visits will be considered "virtual" visits and will be conducted by investigators (or qualified designees) via real-time video conferencing. Other procedures will be performed by qualified nurses who will visit the patients' homes (and/or applicable locations).

If patients have concerns about the virtual nature of the site visits, they may request an unscheduled visit (USV) at the investigational center. The medical monitor will review individual requests and may approve 1 site USV per patient, per year. The assessments at site USVs will mirror those obtained during safety evaluation TCs (see Section 4.6.4). The investigator (or qualified designee) may schedule additional site visits on a case-by-case basis for patients that require closer monitoring due to safety events.

Patients excluded from the study due to lack of internet connection or inability to transition from in-person study visits to virtual study visits may be eligible to enroll in the Open-PRIDE-HD study (Study TV7820-CNS-20016).

#### **4.6.1 Virtual Transition Visit**

The signing of an informed consent form (ICF) and the VTV will be held at the time of the patient's last in-person Open-HART study visit and within 30 days prior to the RV1. Patients may not transition from in-person visits to remote visits before signing informed consent.

After signing informed consent and confirmation of the ability to perform virtual study visits, patients will transition from in-person study visits to remote visits in the Open-HART study.

During the VTV the patient will be asked to appoint a research proxy (see Section 9.2)

IMP will be dispensed at the VTV. All subsequent IMP dispensation will be shipped directly to the patient.

Investigators (or qualified designees) will be trained on video conferencing equipment and remote connection techniques for administration of assessments prior to the patient's first test connection. Patients will be provided with a tablet for remote video conferencing visits after they have completed their last in-person visit and provided written informed consent. A test connection will be completed at the patient's home (and/or applicable location) by the vendor prior to the RV1 to ensure that the investigational site and patient video conferencing equipment are working properly.

#### **4.6.2 First Remote Visit**

The RV1 is to be completed within 30 days of the VTV. This visit will be the first virtual visit of the study and will be completed via remote video conferencing. Safety and tolerability will be assessed at all visits of treatment until the end of patient participation, including the follow-up and End-of-Study (EOS) visits. Assessments will be performed according to Section 1.3.

---

#### **4.6.3 Remote Video and Mobile Nurse Visits**

Additional remote video visits will be performed at Weeks 26, 52, and every 26 weeks thereafter (as well as for USVs) until study discontinuation. During these virtual visits, inquiries about AEs, concomitant medication (including changes in use of benzodiazepines and antidepressants), changes in use of alcohol and drugs associated with substance abuse (legal or illicit); an evaluation for research study consent; C-SSRS collection; abbreviated PBA-s collection (a subset of PBA-s questions on depressed mood, suicidal ideation, anxiety, irritability, loss of motivation, and obsessive-compulsive behaviors); and the UHDRS will be conducted by the investigator (or qualified designee). The UHDRS will only be collected at remote visits every 52 weeks and at EOS/ET or USVs. The abbreviated PBA-s will be collected at visits when the UHDRS (Behavior) is not collected.

Remote video visits will be accompanied by an in-person visit from a mobile nurse (within 7 days). Mobile nurses will perform safety laboratory tests, pregnancy tests, vital sign measurements, ECGs, weight, and IMP accountability at the patient's residence (and/or other applicable location) at the time points listed in Section 1.3.

#### **4.6.4 Safety Evaluation Telephone Contacts**

Safety evaluation TCs will be conducted by the investigator (or qualified designee) between remote visits at Weeks 13, 39, 65, 91, and every 13 weeks thereafter as well as at unscheduled visits (USVs). During these TCs, inquiries about AEs, concomitant medication (including changes in the use of benzodiazepines and antidepressants), changes in use of alcohol and drugs associated with substance abuse (legal or illicit), an evaluation for research study consent, C-SSRS collection, and abbreviated PBA-s collection will be conducted by the investigator (or qualified designee). The investigator (or qualified designee) will also discuss IMP compliance with the patient during each TC. Assessments will be collected according to Section 1.3.

#### **4.6.5 Unscheduled Visit(s)**

USVs may occur as needed and can be completed via remote video, in-person visit, or TC (TC will be the primary form of contact; remote video or in-person visits may be scheduled at the discretion of the investigator [or qualified designee]). The USV may be used to perform assessments per the investigator's (or qualified designee's) judgement. The following assessments are required at an USV: AE review and concomitant medication inquiry. An USV may also be used to re-consent a patient, if necessary.

If patients have concerns about the virtual nature of site visits, he/she may request an USV at the site. The medical monitor will review individual requests and may approve 1 site USV per patient per year. The assessments at site USVs will mirror those obtained during safety evaluation TCs (see Section 4.6.4). The investigator (or qualified designee) may schedule additional site visits on a case-by-case basis for patients that require closer monitoring due to safety events.

If a patient has tolerability problems, or has to de-escalate the investigational medicinal product (IMP), the investigator (or qualified designee) can decide to call the patient to an USV at the investigational center. Patients should be advised that if tolerability problems continue, then they should contact their investigator (or qualified designee) who may then withdraw them from the IMP (see Section 7.7.2).

If a patient attends an USV between the scheduled visits, they should be instructed to attend their next visit according to the study schedule as planned.

#### **4.6.6 End of Treatment Visit**

This visit will be completed in place of the Early Termination (ET) visit when a patient is no longer able to receive IMP for various reasons but wishes to remain in the study. Patients who discontinue IMP due to safety or tolerability reasons, or the inability to complete virtual visits, may remain enrolled in the study without treatment at the discretion of the investigator (or qualified designee). Patients should complete the end-of-treatment (EOT) visit and continue with scheduled visits and assessments until the end of study (EOS) or ET. For subsequent visits, these patients will follow the Schedule of Assessments for the remaining remote video/mobile nurse and safety evaluation TC visits.

#### **4.6.7 End of Study/Early Termination Visit**

Patients who complete all scheduled visits (remote video and TC) will have procedures and assessments performed via remote video conference and mobile nurse visit at the EOS/ET visit. Patients who withdraw from the study before completing the treatment period will have the EOS visit (or ET) procedures and assessments performed at his/her final visit.

The end of study is defined as the last visit of the last patient.

#### **4.6.8 Follow-up**

All patients will be followed for safety via TCs.

#### **4.6.9 Withdrawal From Treatment**

If the patient wishes to stop treatment, is judged by the investigator (or qualified designee) to not be suitable for continued therapy, or the study is discontinued, a remote visit ("withdrawal visit", ET visit) should be performed and the patient withdrawn from the study. A (telephone) follow-up visit (30 d TC follow up) to collect and report AEs, concomitant medications (as well as inquiry about changes in use of benzodiazepines and antidepressants), changes in use of alcohol and drugs associated with substance abuse (legal or illicit), C-SSRS, and an abbreviated PBA-s assessment should take place 1 month after the actual discontinuation of IMP took place.

Additional criteria for discontinuation of IMP for individual patients are detailed in Section [7.7.1](#).

Patients who discontinue IMP due to safety or tolerability reasons may continue in the study off IMP and perform the scheduled visits and assessments.

#### **4.6.10 Study Duration**

The study will continue until:

- the IMP has been authorized for marketing by the respective regulatory authority in Canada or the US; *or*
- the study is discontinued for medical/scientific (risk-benefit) or commercial reasons.

### **4.7 Definition of Assessments**

#### **4.7.1 UHDRS**

Components of the UHDRS ([Huntington Study Group, 1996](#)) will be assessed, as detailed below. All UHDRS components will be assessed in-person at the VTV, and some components

---

will be assessed virtually at the remote visits (RV1, RV3, and RV5) and the EOS/ET and EOT visits, as well as at any USVs, as needed.

#### **4.7.1.1 Motor**

The UHDRS motor assessment comprises 31 assessments from the 15 items, with each assessment rated on a 5-point scale from 0 (normal) to 4 (maximally abnormal) ([Huntington Study Group, 1996](#)). A modified motor UHDRS will be done, excluding the rigidity, tandem walking, and retropulsion pull test tasks.

#### **4.7.1.2 Function**

The functional assessment battery of the UHDRS will be administered. The functional assessment scale assesses 25 items associated with functional problems ([Huntington Study Group, 1996](#)).

This scale assesses 5 functional domains associated with disability (occupation, domestic chores, activities of daily living, care level). Individual domain scores range from 2 or 3 (fully functional) to 0 (severely disable), with a total of 13 points possible ([Huntington Study Group, 1996](#)).

#### **4.7.1.3 Behavior**

This scale measures the frequency and severity of symptoms related to affect, thought content and coping styles. The total behavioral score is the sum of the product (frequency score multiplied by severity score) of all responses. Individual subscales for the various components of the behavioral rating are the product (frequency score multiplied by severity score) for the individual question ([Huntington Study Group, 1996](#)).

#### **4.7.1.4 Independence**

This is a rating scale where a patient's degree of independence is given in percentage (from 0 to 100%); 100% indicated no special care needed and 0% indicated total care required ([Huntington Study Group, 1996](#)).

#### **4.7.1.5 Cognition**

The UHDRS Cognitive assessment battery consists of the Stroop Interference Test, Verbal Fluency Examination, and Symbol Digit Modalities Test.

#### **Stroop Interference Test**

The Stroop Interference test ([Stroop, 1935](#)) measures the ability of the patient to concentrate and ward off distractions. The test consists of 3 items; naming color rectangles (red, green, or blue), reading color words written in black, and naming the color of the ink of incongruent color words. Each test comprises 100 stimuli presented on a card. The test is scored as the number of correct responses made in 45 seconds.

#### **Verbal Fluency Examination**

The verbal fluency examination is part of the cognitive assessment battery of the UHDRS. This test constitutes the Controlled Oral Word Association Test ([Benton et al 1976](#)). This examination consists of a phonological fluency test. The purpose of the test is to examine the ability of the patient to produce a series of words in response to their phonological characteristics, specifically their first letter. The patient is asked to produce as many responses as possible to a specific letter for 60 seconds. The letters will be appropriate for the language used.

---

### **Symbol Digit Modalities Test**

The symbol digit modalities test is part of the cognitive assessment battery of the UHDRS. This test constitutes a digit symbol test (Smith, 1968). The patient is given a template of symbols corresponding to the digits 1-9. The patient has then 90 seconds to write as many correct responses as possible.

#### **4.7.2 Columbia-Suicide Severity Rating Scale**

The C-SSRS is a 2-page questionnaire designed to systematically and prospectively assess and track suicidal AEs (behavior and ideation) throughout clinical studies.

#### **4.7.3 Problem Behaviors Assessment – Short Form**

Because of the prominence of psychiatric symptoms in HD, it is recommended that the PBA-s form be used in all HD studies with any need for behavioral assessment as a comprehensive screen for the most common psychiatric symptoms in HD (Craufurd et al 2001; Kingma et al 2008). The PBA-s is a brief semi-structured interview covering the most common behavioral and psychiatric manifestations of HD. The interview is not restricted to a single construct, but rather covers several broad symptom domains relevant to HD, comprising 11 items: low mood, suicidal ideation, anxiety, irritability, anger/aggressive behavior, loss of motivation, perseverative thinking or behavior, obsessive-compulsive behaviors, paranoid thinking, hallucinations, behavior suggestive of disorientation. Each symptom is rated for severity on a 5-point scale according to detailed scoring criteria, which roughly correspond to the following: 0 = "not at all"; 1 = trivial; 2 = mild; 3 = moderate (disrupting everyday activities) and 4 = severe or intolerable. Each symptom is also scored for frequency on a 5-point scale as follows: 0 = symptom absent; 1 = less than once weekly; 2 = at least once a week; 3 = most days (up to and including some part of everyday); and 4 = all day, every day. Severity and frequency scores are multiplied to produce an overall 'PBA score' for each symptom.

Only the abbreviated PBA-s (i.e. items of the PBA-s relevant to suicidality [depressed mood, suicidal ideation, anxiety, irritability, loss of motivation, obsessive-compulsive behaviors]) will be collected during the TCs and virtual visits when the UHDRS is not completed. If the patient has a positive score 1 and 2 on the suicidal ideation item or depressed mood item of the PBA-s, the patient will be monitored more closely and treated according to the investigator's (or qualified designee's) medical judgment. Patients with C-SSRS or PBA-s suicidality scores 1 and 2 may be handled by investigator (or qualified designee)/neurologist with a consultancy with psychiatrist(s) where necessary per investigator's (or qualified designee's) medical judgement.

A referral for psychiatric evaluation is required for AE/serious adverse event (SAE) of suicidal ideation/suicidal attempt or significant increase in the suicidality scale from baseline (e.g. 2 point increase or higher) or C-SSRS (who answer "Yes" to questions 3, 4, and 5 in the scale suicidal ideation section) or PBA-s suicidality score 3 and above. All patients with PBA-s suicidal ideation item score  $\geq 3$  (i.e. 3, 4) will be discontinued from treatment with IMP. Patients who are discontinued from IMP may continue their participation in the study and perform the scheduled visits and assessments, while off IMP. They will continue to be closely monitored by the investigator (or qualified designee) and will be referred for psychiatric evaluation per the investigator's (or qualified designee's) medical judgment.

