### **7.7.1 Cessation of Treatment**

A patient will be classified as having ceased treatment when he or she discontinues IMP, prior to the completion of the prescribed course for any of the following reasons:

- AE
- Death
- Lost to follow up
- Patient withdrew consent
- Major protocol violation
- Pregnancy

- 
- Treatment is no longer appropriate
  - Termination of study

If hypokalemia is observed, dosing will be interrupted and should not be started again until normal electrolyte values are confirmed by re-draw and maintained for 7 days. Patients needing more than 14 days to reach stable potassium levels, without IMP, should be withdrawn from the IMP. The patient will be asked to continue in the study and follow the visit schedule as outlined in the protocol.

In instances where there is an increase in QT/QTcF of >500ms or 60ms over VTV, a second ECG should be repeated after 10 minutes rest to confirm the finding. Where confirmed, this should be reported and documented on the eCRF as an AE.

Patients with a QTcF interval of >500 ms, or with an increase in the average QTcF value >60 ms from the VTV, should be discontinued from the study. A follow-up ECG should be done in 4 weeks.

Patients should also be discontinued if:

- they experience a seizure or convulsions (regardless of the relationship to treatment);
- their body weight decreases to <50 kg (may be discontinued based on investigator (or qualified designee) or Sponsor discretion);
- and/or if creatinine clearance decreases to <60 mL/min (calculated using the Cockcroft-Gault equation). It is allowed to repeat the test once, if clinically appropriate.
- they experience an AE/SAE of suicide ideation or attempt; or
- they have a C-SSRS suicidal ideation score  $\geq 3$  (i.e. who answer "Yes" to questions 3, 4, and 5 in the scale suicidal ideation section); or
- they have a C-SSRS report of suicidal act; or
- they have an abbreviated PBA-s suicidal ideation item score  $\geq 3$  (i.e. 3, 4).

Patients who discontinue treatment with IMP due to safety or tolerability reasons may continue in the study off IMP and perform the scheduled visits and assessments.

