### **4.3. Scoring for Rating Scales**

A detailed description for all rating scales below can be found in the protocol.

The UHDRS comprises a broad assessment of features associated with HD. It is a research tool which has been developed to provide a uniform assessment of the clinical features and course of HD. The TMS component of UHDRS comprises 31 assessments from the 15 items of the UHDRS. The UHDRS-TMS is calculated as the sum of the 31 motor assessments.

The TFC scale of the UHDRS assesses 5 functional domains associated with disability (occupation, finances, domestic chores, activities of daily living, and care level). The UHDRS-TFC is calculated as the sum of the 5 functional capacity items.

The FA component of the UHDRS assesses 25 items associated with functional problems. The UHDRS-FA is calculated as the sum of the 25 items.

The behavioral assessment of the UHDRS comprises 11 items that measures the frequency and severity of symptoms related to affect, thought content and coping styles. Severity and frequency scores are multiplied (after setting all values outside the range of 0-4 to missing) to produce an overall score for each item. The total behavioral score is the sum of the overall scores across the 11 items.

The PBA-s is a brief semi-structured interview covering the most common behavioral and psychiatric manifestations of HD. The interview is not restricted to a single construct, but rather covers several broad symptom domains relevant to HD, comprising 11 items. Each symptom is rated for severity and for frequency. Severity and frequency scores are multiplied (after setting all values outside the range of 0-4 to missing) to produce an overall 'PBA score' for each symptom. The PBA total score is the sum of all PBA scores across the 11 symptoms.

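### The PBA-s suicidality thresholds do not say which score they use: the only per-symptom score defined (severity × frequency) does not fit the stated values 3 and 4, and severity and frequency both do.

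*Protocol*

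**What the plan says.** **Scoring.** Protocol 4.7.3 gives each PBA-s symptom two ratings, both running 0 to 4: "Each symptom is rated for severity on a 5-point scale according to detailed scoring criteria" and "Each symptom is also scored for frequency on a 5-point scale as follows". It then combines them: "Severity and frequency scores are multiplied to produce an overall 'PBA score' for each symptom". SAP 4.3 likewise multiplies the two ratings "to produce an overall 'PBA score' for each symptom", and SAP 4.4 uses the word item for these products.

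**Thresholds in Protocol 4.7.3.** There are three bands:
- Closer monitoring: "If the patient has a positive score 1 and 2 on the suicidal ideation item or depressed mood item of the PBA-s".
- Psychiatric referral: a PBA-s suicidality score of 3 and above, with no upper end given.
- Stopping study drug: "All patients with PBA-s suicidal ideation item score" of at least 3, glossed as 3 or 4.

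**Protocol 7.7.1** repeats the stopping rule among its discontinuation criteria ("they have an abbreviated PBA-s suicidal ideation item score" of at least 3, same gloss).

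**Exclusion.** Protocol 1.1 and 4.5 exclude patients with a score of at least 3 "on the Problem Behaviors Assessment – Short Form (PBA-s"). No item and no component is named.

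No threshold says whether the score is severity, frequency or their product.

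**The concern.** A stopping threshold should be computable in only one way from the recorded ratings. Here the defined score and the gloss on the threshold do not match, and the gloss fits two different ratings equally well. Two sites with the same severity and frequency ratings for the same patient could therefore act differently: one keeps the patient on drug under closer monitoring, the other stops. This concerns suicidality, in a disease for which Protocol 2.1 reports a raised suicide risk.

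The planned reporting would not reveal the difference. SAP 2.3 lists the PBA-s as a suicidality measure, but SAP 7.8 summarises only the C-SSRS. SAP 6.2 reports the PBA-s as total and domain scores. A product of 4 can come from severity and frequency of 1 and 4, 2 and 2, or 4 and 1, so summaries built from products cannot show who met a threshold on a single rating.

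**Working it through.** **Inputs.** Severity 0–4 and frequency 0–4 (Protocol 4.7.3); symptom score = severity × frequency (Protocol 4.7.3, SAP 4.3); stopping threshold ≥3, glossed as 3 or 4 (Protocol 4.7.3, 7.7.1).

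**Step 1: does the defined score reproduce the gloss?** The possible products are 0, 1, 2, 3, 4, 6, 8, 9, 12 and 16. Those of at least 3 are 3, 4, 6, 8, 9, 12 and 16. The gloss lists only 3 and 4, so the product does not reproduce it. Severity alone does (values ≥3 on a 0–4 scale are 3 and 4), and so does frequency alone.

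**Step 2: the 16 combinations with the symptom present.** Each cell shows the product.

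| | Frequency 1 | Frequency 2 | Frequency 3 | Frequency 4 |
|---|---|---|---|---|
| Severity 1 | 1 | 2 | 3 | 4 |
| Severity 2 | 2 | 4 | 6 | 8 |
| Severity 3 | 3 | 6 | 9 | 12 |
| Severity 4 | 4 | 8 | 12 | 16 |

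**Step 3: combinations stopped under each reading.**
- Severity ≥3: two rows of four = 8 of 16.
- Frequency ≥3: two columns of four = 8 of 16.
- Product ≥3: all except (1,1), (1,2) and (2,1), so 16 − 3 = 13 of 16.

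**Step 4: where the readings part (severity, frequency).**
- Severity against frequency: severity alone stops (3,1), (3,2), (4,1), (4,2); frequency alone stops (1,3), (1,4), (2,3), (2,4). They disagree on 4 + 4 = 8 of 16.
- Product against severity: 13 − 8 = 5 combinations are stopped only by the product: (1,3), (1,4), (2,2), (2,3), (2,4). None is stopped by severity but kept by the product.
- All three agree to stop on 4 combinations, (3,3), (3,4), (4,3), (4,4), and to keep on 3, (1,1), (1,2), (2,1). They agree on 7 and differ somewhere on 16 − 7 = 9.

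**Examples.** Mild ideation at least weekly, (2,2), falls in the monitoring band on either single rating but has product 4. Trivial ideation on most days, (1,3), is kept on severity and stopped on frequency.

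**Step 5: is the exclusion measurable?** In the Amendment 05 schedule (Protocol 1.3), eligibility is checked at the VTV and RV1. The abbreviated PBA-s is marked at neither; it first appears at TC1, Week 13. The exclusion threshold therefore has no scheduled PBA-s measurement behind it.

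**The case against.** The strongest reply is that the meaning is nearly clear. The protocol gives the product its own name, and the thresholds do not use that name. With zero, the bands 1–2 and 3–4 divide a 0–4 rating exactly, so the product is not what was meant. The SAP scoring rules serve analysis and do not instruct sites. Most of this stands. It narrows the question, but it leaves severity against frequency open, and that alone is 8 of 16 combinations. Nor does it remove the risk that a site uses the one symptom score the protocol defines.

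A second reply is that other safeguards apply. Drug also stops for an adverse event of suicidal ideation or attempt, a C-SSRS ideation score of at least 3, or a C-SSRS suicidal act (Protocol 7.7.1), and the C-SSRS and adverse events are reviewed at every scheduled visit. That stands and limits the effect. But 7.7.1 lists the PBA-s criterion as a separate alternative, so it is meant to act by itself.

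A reader might infer four stronger things that the documents do not support:
- **That the threshold is set on the product.** The protocol never says so, and its gloss argues against it.
- **That only a product of exactly 3 or 4 stops drug, so a 4 × 4 rating (product 16) is kept.** This lets the gloss override the operative ≥3, and nothing suggests a site would read it that way.
- **That weekly mild irritability (2 × 2 = 4) excludes a patient.** The exclusion sentence is about suicidality from start to finish. The item is unnamed, but the context implies it.
- **That a primary safety result is distorted.** Long-term safety is the primary objective, but neither document names a suicidality-related discontinuation rate as an endpoint.

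**Conclusion.** The point holds as an ambiguity in a safety threshold. The monitoring, referral and stopping thresholds name no score component; the one per-symptom score defined does not fit the stated values; and the two ratings that fit disagree on 8 of 16 combinations. Use of the defined product would stop 13 of 16, against 8 under either single rating. The exclusion criterion is looser still, naming neither item nor component.

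The counts give every combination equal weight. The documents give no distribution of PBA-s ratings, so the number of patients affected cannot be derived. The detailed severity scoring criteria that 4.7.3 mentions are not reproduced in the protocol text and might narrow the reading.

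All the protocol wording cited is from Amendment 05, and SAP 2.1 says that amendment was not implemented and that the SAP rests on Amendment 04. An effect on the study as conducted is therefore not shown. The question still matters there, because the design described in SAP 2.1 also collects the PBA-s.

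This should be corrected. It is a wording defect with a bounded effect, and which component is right is a clinical decision outside this review.

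**What to change.** 1. Reconcile Protocol 1.1, 4.5, 4.7.3 and 7.7.1 so that every PBA-s suicidality threshold (monitoring, referral, discontinuation, exclusion) names the item, the score component (severity, frequency or product) and its full range. The sponsor's clinical team chooses the component.
2. Have the eCRF derive the flag from the two recorded ratings, so that sites do not compute it by hand.
3. Reconcile the exclusion with the schedule: state which PBA-s assessment it relies on, since none is marked at the VTV or RV1.
4. Check the Amendment 04 wording for the same rule, and state in the study report which reading the sites applied.

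The cost is protocol wording, one eCRF derivation or edit check, and a short statement in the report. Items 1, 2 and 4 need no new assessment; item 3 needs only a clarification unless the sponsor decides otherwise.
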